7.5.4 Multiplicity Adjustment

The overall confidence level for the study in demonstrating non-inferiority is 95%, which is equivalent to 5% of Type I error. Type I error of 0.7% will be allocated for the 6 month analysis which is equivalent to 99.3% confidence interval. The final alpha depends on the observation of data and it is expected that 0.048 will keep the overall alpha level at 5% based on data from study 017 and 057. Type of I error of 0.048 is equivalent to a 95.2% confidence interval.

With the significant reduction of sample size due to the early stop of enrolment of the study, there is insufficient power to demonstrate non-inferiority of the two treatment regimens. Hence, the adjustment of alpha between 6 months and 12 months PFS rates will not be conducted. Instead, 95% one-sided confidence interval around the difference of PFS rates will be generated.

7.5.5 Efficacy Analyses By Subgroup

PFS rates at 6, 12 and 24 months and corresponding two-sided 95% CI for each treatment arm, along with the one-sided 95% CI for the difference of PFS rates at 6, 12 and 24 months between the treatment arms will be calculated for the following subgroups using the same method as for PFS rate described in the primary efficacy analysis.

- Gender (male vs. female)
- Age categorization (< 65 vs. ≥ 65)
- Baseline ECOG PS (0,1, 2)
- EGFR mutation status (positive vs. not detected vs. not reported)
- Line of prior therapy (first line vs. ≥ second line)
- Duration of prior Nivolumab treatment (< 3 months, 3 - < 6 months vs. ≥ 6 months)
- Stratification factors (Histology [Sq vs. Non-Sq]; response criteria to pre-study nivolumab at randomization (CR or PR vs. SD)

OS rates at 6, 12, 18, 24, and 36 months will also be summarized by treatment arms using the same method as for PFS rate described in the primary efficacy analysis for the above subgroups.

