## 1 INTRODUCTION AND STUDY RATIONALE

The approved treatment options for locally advanced or metastatic non-small cell lung cancer (NSCLC) have been limited. Approximately 85% of lung cancer is NSCLC. Of these, approximately 80% are non-squamous (non-Sq) and 20% are squamous (Sq) histology.

Despite treatment with platinum- and taxane-based chemotherapy, patients with metastatic NSCLC have a median overall survival (OS) of 10 months and a 5-year survival rate of ~15%. Data are emerging that suggest patients with SqNSCLC may have a worse prognosis and fewer therapeutic options than patients with other histologies. Pivotal studies of first-line and second-line therapy have indicated that, in contrast to non-SqNSCLC, patients with SqNSCLC do not derive benefit from newer agents such as pemetrexed or bevacizumab. Similarly, activating mutations in epidermal growth factor receptors (EGFR) that render lung tumors sensitive to EGFR-targeted tyrosine kinase inhibitors (EGFR-TKIs) are found in only approximately 2.7% of SqNSCLC cases.

Despite the increased number of treatment options available for patients with non-SqNSCLC, there have been little OS improvements from several new agents, including pemetrexed and bevacizumab. Therapeutic options for mutation wild-type non-SqNSCLC are particularly limited after failure of front-line chemotherapy. With the development of targeted agents for patients with tumors with driver mutations in the EGFR or anaplastic lymphoma kinase (ALK), some improvement in progression-free survival (PFS) is realized, but, as a consequence of acquired resistance, the improvement in OS is still limited. Overall, this group of patients only has an OS of about 8 months after progression from platinum agents. Once resistance to TKIs occurs, the patients who have EGFR mutations or ALK translocations will have rapid disease progression.

Nivolumab (BMS-936558) is a fully human, IgG4 (kappa) isotype mAb that binds PD-1 on activated immune cells and disrupts engagement of the receptor with its ligands PD-L1 (B7 H1/CD274) and PD-L2 (B7-DC/CD273), thereby abrogating inhibitory signals and augmenting the host antitumor response. In early clinical trials, nivolumab has demonstrated activity in several tumor types, including melanoma, renal cell carcinoma (RCC), and nonsmall cell lung cancer (NSCLC).

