7.5 Efficacy

7.5.1 Primary Efficacy Analysis

The coprimary objectives will be assessed by PFS rate at 6 months and PFS rate at 12 months. PFS will be summarized by Kaplan-Meier product-limit method for all randomized patients. Median values of PFS, along with two-sided 95% CI using Brookmeyer and Crowley method (a log-log transformed CI for the survivor function $S(t)^{2,3}$, will be calculated for each treatment arm.

The hazard ratios between treatment arms along with the one-sided 95% CI will be produced from a stratified Cox proportional hazard model (by tumour histology [Sq vs. Non-Sq] and response category at randomization [CR or PR vs. SD]).

PFS rates at 6 months and 12 months will be calculated using KM estimates on the PFS curve for each randomized treatment arm. Minimum follow-up must be longer than the time point to generate the rate. The two-sided 95% CIs, adjusted for stratifying factors (by tumor histology (Sq vs. Non-Sq), response criteria (CR or PR vs. SD) using inverse variance weight, for PFS rates at 6 months and 12 months will be calculated for each treatment arm, along with one-sided 95% CI for the difference between the two treatment arms using the Greenwood formula⁴ for variance derivation. Denote $\hat{S}_i(t)$ as an estimate of survival function from Kaplan-Meier estimate and

$\hat{Var}(S_i(t))$ as the variance of estimation for stratum i at time t, respectively, w_i as the weight for

stratum i, defined as
$$\frac{1/\hat{Var}(\hat{S}_i(t))}{\sum_{i=1}^k [1/\hat{Var}(\hat{S}_i(t))]}$$
 where k is the number of strata (k = 4). Then the weighted

survival estimate for PFS rate across all the strata at time t is
$$\sum_{i=1}^k w_i \hat{S}_i(t)$$
 and weighted variance of

estimation is
$$\hat{\sigma}_w^2 = \frac{1}{\sum_{i=1}^k 1/\hat{Var}(\hat{S}_i(t))}$$
. The two-sided 95% CIs for the PFS rates for each treatment

arm will be calculated as
$$\sum_{i=1}^k w_i \hat{S}_i(t) \pm z_{(1-\alpha/2)} \times \hat{\sigma}_w$$
, where $\alpha=0.05$.

The estimated PFS rate difference at time t between two treatment arms is
$$\hat{S}_{E_i}(t) - \hat{S}_{C_i}(t)$$
, where

$\hat{S}_{E_i}(t)$ is the estimated PFS rate for 480 mg every 4 weeks treatment arm (Arm2) for stratum i

and $\hat{S}_{C_i}(t)$ is the estimated PFS rate for 240 mg every 2 weeks treatment arm (Arm 1) for stratum i. The variance for PFS rate difference between two treatment arms at time t for stratum i

is
$$\hat{Var}(\hat{S}_{E_i}(t)) + \hat{Var}(\hat{S}_{C_i}(t))$$

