. Denote w_i as the weight for stratum i, defined

as
$$\frac{1/[\hat{Var}(\hat{S}_{E_i}(t)) + \hat{Var}(\hat{S}_{C_i}(t))]}{\sum_{i=1}^k \left\{ 1/[\hat{Var}(\hat{S}_{E_i}(t)) + \hat{Var}(\hat{S}_{C_i}(t))] \right\}}$$
 where k is the number of strata (k = 4). Then the weighted

estimate for PFS rate difference between two treatment arms across all the strata at time t is

$$\sum_{i=1}^k w_i (\hat{S}_{E_i}(t) - \hat{S}_{C_i}(t))$$
 and weighted variance of estimation

is
$$\hat{\sigma}_w^2 = \frac{1}{\sum_{i=1}^k 1/[\hat{Var}(\hat{S}_{E_i}(t)) + \hat{Var}(\hat{S}_{C_i}(t))]}$$
. The one-sided 95% CIs for the difference of PFS rates

between two treatment arms will be calculated as
$$\left(\sum_{i=1}^k w_i (\hat{S}_{E_i}(t) - \hat{S}_{C_i}(t)) - z_\alpha \times \hat{\sigma}_w, 1 \right)$$
, where $\alpha=0.05$.

The source of progression (death vs. progression) will be summarized by treatment arm.

The status of subjects who are censored in the PFS Kaplan-Meier analysis will be tabulated for each treatment group using following categories:

- On-study (on treatment, in follow-up)
- Off-study: (lost to follow-up, withdrew consent, other).
- No baseline tumor assessment and no death
- No on-study tumor assessment and no death

For the 6-month analysis, the 99.3% one-sided adjusted CI around the difference in PFS rates between two treatment arms will be generated using the inverse variance weight method as above where $\alpha=0.007$. If the lower bound of the CI is above -10%, non-inferiority will be claimed.

A 95.2% adjusted CI around the difference in PFS rates at 12 months will be generated using the same approach for 6-month analysis where $\alpha=0.048$. If the lower limit of the CI is above -10%, it is considered that the Arm 2 (Q4W) is non-inferior to Arm 1 (Q2W).

Due to the early stop of enrolment of the study, approximately 350 subjects are expected to be randomized and receive study treatment. With the significant reduction of sample size, there is insufficient power to demonstrate non-inferiority of the two treatment regimens. Hence, the adjustment of alpha between 6 months and 12 months PFS rates will not be conducted. Instead, 95% one-sided confidence interval around the difference of PFS rates will be generated.

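### SAP 7.5.5 carries the four-stratum inverse-variance method into small subgroups with no rule for empty or zero-variance strata, so their results are often undefined or their difference intervals too narrow

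*SAP*

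**What the plan says.** SAP 7.5.5 covers PFS rates at 6, 12 and 24 months in each listed subgroup. Arm rates get two-sided 95% intervals and differences get one-sided 95% intervals, and these "will be calculated for the following subgroups using the same method as for PFS rate described in the primary efficacy analysis". The same pointer governs OS: "OS rates at 6, 12, 18, 24, and 36 months will also be summarized by treatment arms". The splits are sex, age, ECOG status, EGFR status, line of therapy, duration of prior nivolumab, and the two randomization factors: "Stratification factors (Histology [Sq vs. Non-Sq]; response criteria to pre-study nivolumab at randomization (CR or PR vs. SD".

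The method pointed to is in SAP 7.5.1. Arm intervals are adjusted for the stratifying factors "using inverse variance weight, for PFS rates at 6 months and 12 months will be calculated for each treatment arm". The weighted difference follows, with a "one-sided 95% CI for the difference between the two treatment arms using the Greenwood formula". Both sums run over all strata, "where k is the number of strata (k = 4"). The only stated condition for reporting a rate is this: "Minimum follow-up must be longer than the time point to generate the rate". There is no rule for an empty stratum, a zero-variance stratum, collapsing of strata, or a minimum subgroup size.

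Unadjusted PFS-rate intervals appear in SAP 7.5.3 as a sensitivity analysis. SAP 7.1 describes fixed-time rates in general terms, from Kaplan-Meier with Greenwood variance and no mention of stratum weights.

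**The concern.** Inverse-variance weighting needs a positive variance estimate in every stratum. Greenwood's variance is zero when the Kaplan-Meier estimate at the time point is 1 or 0, and it does not exist in an empty cell. With about 350 subjects in two arms and four strata, a subgroup of modest size has cells of a few patients. The formula can then divide by zero. It can also return a number in which a tiny cell gets a large weight because its variance happens to be underestimated.

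The stakes are the subgroup results and one secondary endpoint: 1-year PFS by histology and by response (SAP 4.2) is not covered by SAP 7.5.2, so 7.5.5 is its only analysis text. Without a written rule, a programmer has to drop or collapse strata after seeing which cells lack events, in an open-label trial.

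**Working it through.** **Plan's own figure.** The SAP gives no figure for subgroups. Its sample size can be checked: n per arm = 2 x 0.48 x 0.52 x (1.665 + 0.842)² / 0.10² = about 314, against the stated 310. The binomial variance is therefore a fair stand-in for the plan's 12-month calculation.

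**What follows without simulation.**
- Subgroup levels: 2 (sex) + 2 (age) + 3 (ECOG) + 3 (EGFR) + 2 (line) + 3 (duration) + 2 (histology) + 2 (response) = 19. With 3 PFS and 5 OS time points, 19 x 8 = 152 result sets. In the 4 histology and response levels (4 x 8 = 32 sets, 21%), two of the four strata are empty by definition.
- Stratum weight for the difference: 1/[Var(S_E) + Var(S_C)]. It is 1/0 when both arms have zero variance. The arm-level weight is 1/0 as soon as that arm's own variance is zero. A one-patient cell with complete follow-up always has zero variance.
- Take a cell of 4 patients with a true rate of 0.60. The chance of zero variance is 0.60⁴ + 0.40⁴ = 0.16. At 0.36 it is 0.36⁴ + 0.64⁴ = 0.18.
- Weight example for a stratum with 4 patients per arm and true rate 0.60. The true summed variance is 2 x 0.24/4 = 0.12, a weight of 8.3. If 4/4 and 3/4 are observed, it is 0 + 0.1875/4 = 0.047, a weight of 21. The stratum gets about 2.6 times its proper weight because its variance is underestimated.
- EGFR-positive squamous subjects: Protocol section 1 puts squamous at about 20% of NSCLC and says that activating EGFR mutations are "found in only approximately 2.7% of SqNSCLC cases". 350 x 0.20 x 0.027 = about 2 subjects, to fill four arm-by-response cells. These are general background figures, not trial data.

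**Simulation A.** Assumed: equal arms, strata 10/10/40/40%, 12-month PFS 0.60 (CR/PR) and 0.36 (SD), no censoring before 12 months. Coverage is for the one-sided 95% bound, among trials where it exists.

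| Per arm | Difference undefined | Coverage, 7.5.1 formula | Coverage, unstratified |
|---|---|---|---|
| 20 | about 75% | about 85% | about 94% |
| 44 | about 13% | about 89% | 94-95% |
| 88 | under 0.5% | about 93% | about 94% |
| 175 (all) | – | 94.2% | 95.0% |

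At 44 per arm, a given arm's rate is undefined in about 42% of trials, and at least one arm's in about 67%. The empirical SD of the difference is 0.128 and the mean reported SE is 0.096, a ratio of 0.75; the unstratified SD is 0.107. Silently dropping the bad strata does not help (coverage 88.7%).

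**Simulation B.** Actual Kaplan-Meier with Greenwood variance, the SAP's PFS rates (0.63 and 0.48) in all strata, assumed censoring of 1% per month, squamous 20-30%, CR/PR 40-50%. Ranges are over 6 and 12 months and both mixes.

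| Per arm | Difference undefined | Arm rate undefined | Coverage, 7.5.1 formula | Coverage, unstratified |
|---|---|---|---|---|
| 175 | 0% | 0-1% | about 94% | 94-95% |
| 88 | 0-2% | 1-11% | 92.4-93.5% | about 95% |
| 60 | 0-10% | 6-29% | 90-92% | 94-95% |
| 35 | 8-40% | 31-64% | 86-88% | 94-95% |
| 18 | 55-86% | 82-93% | 81-86% | 93-94% |

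**Histology and response subgroups over their two real strata** (simulation A assumptions, 12-month PFS): difference undefined in 0.0% at all four levels, coverage about 93-95%.

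**Early OS.** With 6-month OS of 0.96 (CR/PR) and 0.90 (SD) assumed, the difference is undefined in about 88% of trials at 44 per arm and about 27% in the full set. With 0.92 throughout, it is undefined in 77-88% at 35 per arm, 24-46% at 88 and 3-14% at 175. Under the first assumption, coverage where the difference exists is near nominal (about 94%).

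**The case against.** The strongest reply is that 7.5.5 may never have meant the weighted formula. SAP 7.1 sets plain Kaplan-Meier and Greenwood as the general approach. SAP 7.5.2 first applies the PFS-rate method to OS and then lists the stratum-adjusted rates as an additional calculation, which suggests that the unqualified phrase means the unadjusted one. This has some force and cannot be ruled out. It does not override 7.5.5, which points to the primary efficacy analysis, where the only rate intervals described are the adjusted ones. If the unadjusted method was intended, a sentence settles it.

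Three further points stand. Half-trial splits are little affected for PFS. Within the histology and response subgroups, taking k as the number of strata present (two) repairs the calculation, so a reader who infers that the secondary comparison cannot be produced goes too far. And non-inferiority is no longer tested, so no decision rule depends on these intervals.

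A reader might also infer that most subgroup results are undefined and that all the others under-cover. The documents do not support that. They give no subgroup sizes, stratum mix or OS rates, and the failures concentrate in small subgroups and at early OS time points.

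**Conclusion.** The point holds in limited form. On its plain reading, 7.5.5 specifies a method that is often undefined or too narrow in small subgroups, and no fallback is written. At 44 per arm, under the stated assumptions, coverage of the 12-month PFS difference falls from 94-95% unstratified to about 89%, with about 13% undefined; at 20 per arm it is about 85%, with about 75% undefined. At half-trial size the PFS effect is small. For 6-month OS the estimate fails to exist; the interval is not too short where it does exist. An event-free stratum in one arm alone makes that arm's rate undefined but leaves the difference defined, with too small a variance.

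The sizes rest on assumed stratum shares, subgroup sizes, rates by response and OS rates. The direction for small subgroups does not depend on one choice, since both simulations show it. It would be wrong to extend the point to the co-primary PFS analysis: in all randomized subjects coverage is about 94%, and the difference is essentially always defined.

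**What to change.** In SAP 7.5.5, replace the reference to the primary-analysis method with the unadjusted Kaplan-Meier/Greenwood method of 7.1 and 7.5.3: arm rates with two-sided 95% intervals, and the unstratified difference with its one-sided 95% bound. Do not prescribe a log-log interval for the rates. The unadjusted-rate text in 7.5.3 does not specify one, and it is itself undefined when Kaplan-Meier is 1 or 0.

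For the adjusted all-randomized OS rates in 7.5.2, state in advance how strata are collapsed when an arm-by-stratum cell is empty or has zero Greenwood variance. Leave the co-primary PFS weighting as it is.

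The cost is about two sentences; 7.5.3 already requires the unadjusted PFS calculation. The downside is that subgroup estimates are no longer adjusted for the stratification factors. Very small subgroups stay imprecise: unstratified coverage in simulation B was about 93% at 9 per arm.

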7.6 Safety

The evaluation of safety is based on the incidence of deaths, adverse events (AEs), serious adverse events (SAEs), AEs leading to discontinuation, AEs leading to dose delay, immune mediated adverse events (IMAEs), select AEs, other events of special interest, vital signs, and specific laboratory abnormalities (worst grade) in each treatment arm. Safety results will be summarized in all treated subjects by treatment arms and overall population unless otherwise specified. All AEs, SAEs, drug-related AEs, and drug-related SAEs will be summarized using the worst grade per NCI CTCAE v4.0 by system organ class and preferred term. Laboratory abnormalities including hematology, chemistry, liver function, thyroid function, and renal function will be summarized using worst grade per NCI CTCAE v4.0 criteria.

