#### **4.5 Selection and Timing of Dose for Each Subject**

Subjects will be enrolled after receiving up to 12 months (52 weeks) of nivolumab therapy at 240 mg or 3 mg/kg Q2W and after achieving a CR, PR, or SD, confirmed on 2 consecutive tumor assessments.

Subjects in Arm 1 will receive 240 mg of nivolumab intravenously as a 30-minute ( $\pm$  5 minutes) IV infusion on Day 1 of each treatment cycle every 2 weeks, until progression, unacceptable toxicity, withdrawal of consent, or the subject reaches a maximum of 2 years from the first on-study dose, or the study ends, whichever occurs first. In this arm, each 14-day dosing period will constitute a cycle.

Subjects in Arm 2 will receive 480 mg nivolumab as a 30-minute ( $\pm$  5 minutes) IV infusion on Day 1 of each treatment cycle every 4 weeks until progression, unacceptable toxicity, withdrawal of consent, or the subject reaches a maximum of 2 years from the first on-study dose, whichever occurs first. In this arm, each 28-day dosing period will constitute a cycle.

Subjects in Arm 1 may be dosed no less than 12 days from the previous dose; subjects in Arm 2 may be dosed no less than 26 days from the previous dose.

No dose escalations or reductions of nivolumab are allowed. There are no premedications recommended for nivolumab until infusion reactions have been observed in the subject. Subjects should be carefully monitored for infusion reactions during nivolumab administration. If an acute infusion reaction is noted, subjects should be managed according to [Section 4.5.5](#).

Dose delay criteria, criteria to resume treatment, and dose discontinuation criteria can be found in [Section 4.5.1](#), [Section 4.5.2](#), and [Section 4.5.3](#), respectively.

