##### **4.5.1 Dose Delay Criteria**

Nivolumab administration should be delayed for the following:

- Grade 2 non-skin drug related AEs, with the exception of fatigue
- Grade 2 drug-related creatinine, AST, ALT and/or Total Bilirubin abnormalities
- Any Grade 3 skin, drug-related AE
- Any Grade 3 drug-related laboratory abnormality, with the following exceptions:
  - Grade 3 lymphopenia or asymptomatic amylase or lipase does not require dose delay
  - Grade  $\geq$  3 AST, ALT, Total Bilirubin will require dose discontinuation

- Any AE, laboratory abnormality, or intercurrent illness which, in the judgment of the investigator, warrants delaying the dose of study medication.

Subjects who require delay of nivolumab should be re-evaluated weekly or more frequently if clinically indicated and resume nivolumab dosing when re-treatment criteria are met.

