**Table 5.1-2: On-Treatment Assessments (CA209384)**

Procedure a	Every Cycle (± 2 days)	Every 4 Weeks (± 2 days)	Every 6 Weeks (± 2 days)	Every 8 Weeks (± 2 days)	Every 6 Months (± 2 days)	End of Treatment	Notes
Safety Assessments							
Physical Examination	X						
Vital Signs	X					X	Within 72 hours prior to dosing and at EOT. Include temperature, BP, HR, RR, O2 saturation by pulse oximetry (at rest preferred) prior to dosing and at any time there are new or worsening respiratory symptoms.
ECOG PS	X						Within 72 hours prior to each dose
Assessment of Signs and Symptoms	X						
Serious Adverse Event Assessment	X						Assessed using NCI CTCAE v. 4.0
Adverse Events Assessment	X						Assessed using NCI CTCAE v. 4.0
Laboratory Tests: hematology tests	X						Includes WBC count with differential, ANC, lymphocyte count, hemoglobin, hematocrit, and platelet count. Results should be available prior to dosing.
Laboratory Tests: chemistry tests	X						Chemistry (BUN or urea, creatinine, sodium, potassium, calcium, magnesium, phosphate, chloride, and glucose), LDH. Results should be available prior to dosing.
Laboratory Tests: liver function test	X						Includes AST, ALT, total bilirubin, alkaline phosphatase, albumin. Completed within 72 hours of dosing. Results should be available prior to dosing.

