### **8.4.3 Safety Analyses**

Safety will be analyzed through the incidence of deaths, AEs, SAEs, AEs leading to discontinuation, AEs leading to dose interruption, select AEs, and specific laboratory abnormalities (worst grade) in each arm. Toxicities will be graded using the NCI CTCAE version 4.0.

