2.1 Study Design

This is an open-label, randomized phase IIIb/IV dose frequency optimization trial in adult patients with advanced/metastatic (Stage IIIb/IV) NSCLC (non-Sq and Sq). Subjects will have received approximately up to 12 months (52 weeks) of nivolumab therapy at either 3 mg/kg or 240 mg every 2 weeks and achieved a complete response (CR), partial response (PR), or stable disease (SD) as evidenced by 2 consecutive tumor assessments prior to enrollment. At enrollment, subjects will be randomized 1:1 to receive either 240 mg every 2 weeks (Arm 1) or 480 mg every 4 weeks (Arm 2). Randomization will be stratified by histology (Sq vs. Non-Sq) and response criteria to pre-study nivolumab at randomization (CR or PR vs. SD). For subjects receiving nivolumab 240 mg every 2 weeks, each 14-day dosing period will constitute a cycle. For subjects receiving nivolumab 480 mg every 4 weeks, each 28-day dosing period will constitute a cycle.

Subjects will continue treatment until disease progression or unacceptable toxicity for a maximum of 2 years from first randomized dose. The follow-up period begins when the decision to permanently discontinue a subject from study therapy is made (no further treatment or retreatment with nivolumab is anticipated). All subjects who discontinue study drug should comply with protocol specified follow-up procedures as outlined in Section 5 of the Clinical Protocol until death or the conclusion of the study. The only exception to this requirement is when a subject withdraws consent for all study procedures including post-treatment study follow-up or loses the ability to consent freely.

The study design schematic is presented in [Figure 2.1-1](#).

Figure 2.1-1: Study Schema

Each patient’s last study visit will be defined as the last on-treatment or follow-up visit that occurs prior to the date of 3 years after the initiation of randomized therapy. The study will be completed no later than 3 years after the last subject’s first visit.

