6.1.2 Post baseline period

On-treatment AEs will be defined as AEs with an onset date-time on or after the date-time of the first dose of study treatment (or with an onset date on or after the day of first dose of study treatment if time is not collected or is missing). For subjects who are off study treatment, AEs will be counted as on-treatment if the events occurred within 100 days of the last dose of study treatment, unless otherwise specified.

On-treatment evaluations (laboratory tests, pulse oximetry and vital signs) will be defined as evaluations taken after the day (and time, if collected and not missing) of first dose of study treatment. For subjects who are off study treatment, evaluations should be within 100 days of the last dose of study treatment.

Post-treatment AEs will be defined as AEs with an onset date-time 100 days after last dose of study treatment.

Late emergent drug related AEs will be defined as drug related AEs with an onset date greater than 100 days after the last dose of study treatment in subjects off study treatment.

Post-treatment evaluations, if necessary, will be defined as evaluations taken 100 days after last dose of study treatment.

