7.4.2 Modifications of Study Therapy

7.4.2.1 Dose delays

Treatment may be delayed for up to a maximum of 6 weeks from the previous dose. Dose interruption of nivolumab which results in treatment interruption of >6 weeks will require treatment discontinuation, with the following exceptions: dosing interruptions to allow for prolonged steroid tapers to manage drug-related adverse events; dosing interruptions for non-drug-related reasons if approved by the medical monitor. Prior to re-initiating treatment in a subject with a dosing interruption lasting >6 weeks, the Medical Monitor must be consulted. A dose will be considered as actually delayed if the delay exceeds 2 days (i.e., greater than or equal to 3 days from scheduled dosing date). The length of delay is defined as (duration of previous cycle in days – 14) for Arm 1 and (duration of previous cycle in days – 28) for Arm 2. Dose delays will be divided into following categories: 3 - <8 days, 8 - <15 days, 15 - <28, 28 - <42, >=42 days. Reason for dose delay will be retrieved from the case report form (CRF) dosing pages.

The following parameters will be summarized by treatment arm:

- Number of dose delayed per subject, length of delay and reason for dose delay
- Number of subjects with at least one dose delay along with reason for the dose delay.

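### Per-cycle blood tests are twice as frequent in Arm 1 as in Arm 2, so worst-grade laboratory tables can miss more short-lived abnormalities on Q4W even if toxicity is equal

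*SAP*

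**What the plan says.** Protocol Table 5.1-2 lists hematology, chemistry and liver tests in its every-cycle column and ties them to the dose. The hematology note, for example, ends "hemoglobin, hematocrit, and platelet count. Results should be available prior to dosing". Protocol 4.5 says of Arm 1: "In this arm, each 14-day dosing period will constitute a cycle". SAP 2.1 says of Arm 2: "For subjects receiving nivolumab 480 mg every 4 weeks, each 28-day dosing period will constitute a cycle". The thyroid row of the same protocol table asks for TSH every 3 cycles (6 weeks) in Arm 1 and every 2 cycles (8 weeks) in Arm 2.

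On analysis, Protocol 8.4.3 lists "select AEs, and specific laboratory abnormalities (worst grade) in each arm", and SAP 7.6 has: "Laboratory abnormalities including hematology, chemistry, liver function, thyroid function, and renal function will be summarized using worst grade per NCI CTCAE v4.0 criteria". SAP 6.1.2 sets the window: "On-treatment evaluations (laboratory tests, pulse oximetry and vital signs) will be defined as evaluations taken after the day" of first dose, up to 100 days after the last dose. SAP 7.6.11 restricts each table to treated subjects who had the test and sets no condition on how many tests or when. Its subsections (7.6.11.1 to 7.6.11.4) refer to the Core Safety SAP. The exposure-adjusted rates in SAP 7.6.10 are for adverse events, not laboratory values.

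**The concern.** A worst grade is a maximum over whatever samples exist. Dosing frequency is the randomised variable and sampling follows dosing, so the number of samples is tied to the arm. With identical toxicity, the arm sampled twice as often will record more short abnormalities.

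Specific laboratory abnormalities in Arms 1 and 2 are part of a secondary objective (SAP 3.2), and Protocol 1.5 says the results should inform physicians about the safety of less frequent dosing. A lower count on Q4W could reflect fewer draws, less toxicity, or both. The tables described in the available text would not let a reader tell which.

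**Working it through.** **Inputs.** Sampling interval T: 14 days in Arm 1, 28 days in Arm 2 (Protocol 4.5, Table 5.1-2; SAP 2.1). About 350 subjects (Protocol 8.1), so about 175 per arm. Duration and rate of abnormalities are not in the documents and are assumed over a range. Onset is taken as uniform within the cycle and toxicity as equal.

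**Check on the schedule.** The plan gives no detection figure to reproduce. Its TSH intervals do follow from the cycle lengths: 3 × 14 = 42 days (6 weeks) and 2 × 28 = 56 days (8 weeks). Scheduled draws in 52 weeks after the first pre-dose sample: 364/14 = 26 and 364/28 = 13.

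**Detection at scheduled draws.** An abnormality of fixed duration d is seen with probability min(1, d/T).

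| d (days) | Arm 1 | Arm 2 |
|---|---|---|
| 7 | 7/14 = 50% | 7/28 = 25% |
| 14 | 14/14 = 100% | 14/28 = 50% |
| 21 | 100% | 21/28 = 75% |
| 28 or more | 100% | 100% |

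With ±2-day variation in visits the result is nearly the same: 94% v 50% at 14 days and 100% v 97% at 28 days. For TSH, a 28-day abnormality is seen 28/42 = 67% v 28/56 = 50%.

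**Illustration of incidence (rates and durations assumed).** For exponential duration with mean m, detection is P = (m/T)(1 − exp(−T/m)), and one-year incidence is 1 − exp(−rate × P). With m = 14, P = 0.632 v 0.432. At 0.30 episodes per patient-year this gives 1 − exp(−0.30 × 0.632) = 17.3% v 1 − exp(−0.30 × 0.432) = 12.2%, a gap of 5.1 points. The standard error at 175 per arm is √[(0.173 × 0.827 + 0.122 × 0.878)/175] = 3.8 points. Over rates of 0.05 to 0.30 and means of 7 to 56 days, the gap runs from 0.5 points (4.3% v 3.9%, before rounding) to 5.1 points, or 0.2 to 1.6 standard errors.

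**How to thin Arm 1.** The obvious device is to keep only odd-numbered Arm 1 cycles. It fails when the abnormality itself holds the dose, as Protocol 4.5.1 and 4.5.2 provide for several laboratory findings. An abnormality of 14 days or more is found at the next draw, which is an even cycle half the time. That sample is dropped, dosing waits for recovery, and the next odd-cycle sample is normal. Arm 1 therefore counts 50% at any such duration, while Arm 2 counts min(1, d/28).

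Thinning by date avoids this. If weekly re-evaluation samples are eligible, an abnormality found between kept dates is sampled again on the next kept date if it is still present. On an exact schedule both arms then count min(1, d/28).

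Simulation with the dose held to recovery and weekly re-evaluation, Arm 1 v Arm 2:

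| d (days) | Odd-cycle rule | 26-day spacing rule |
|---|---|---|
| 21 | 49% v 72% | 75% v 70% |
| 28 | 49% v 96% | 99% v 95% |
| 42 | 51% v 100% | 100% v 100% |

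The odd-cycle rule creates a roughly two-fold gap against Q4W at durations where the full table has almost none. The spacing rule keeps the arms within 5 points.

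**The case against.** The strongest objection is that the gap in the plan is not established: hematology, chemistry, electrolytes and additional laboratory analyses all defer to a Core Safety SAP that was not available. This stands. The point is that no adjustment is visible, and the fix gives way if one exists.

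Second, the consequence is limited. SAP 3.2 sets out to assess safety, where its PFS and OS objectives say compare. The laboratory tables carry no test, margin or decision, and the largest illustrated gap is 1.6 standard errors. This also stands and keeps the point minor. The effect is nonetheless systematic, and readers of descriptive tables compare counts directly.

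Third, unscheduled testing narrows the gap. Protocol 4.5.1 says: "Subjects who require delay of nivolumab should be re-evaluated weekly or more frequently if clinically indicated". That starts only once a delay is required, so a silent short abnormality must first be sampled. Protocol 5.3 also tells sites not to submit additional standard-of-care assessments unless asked.

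Fourth, equal spacing does not equalise time since the last dose, which is about 14 days in Arm 1 and 28 in Arm 2. This is correct and must be stated with the table.

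A reader might also use the CA209057 Grade 3-4 laboratory rates in Protocol 1.4.2 to predict how many cases Q4W would miss. The documents do not support that. Those patients were starting nivolumab, whereas subjects here have already received and tolerated it and must meet laboratory entry limits. The CA209057 testing schedule and the durations are not given either.

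**Conclusion.** The concern holds in limited form. Scheduled sampling differs two-fold for hematology, chemistry and liver tests. With equal toxicity, abnormalities shorter than about 28 days are less likely to appear in the Q4W worst-grade table: half as likely up to 14 days, then converging by 28. This assumes uniform onset and detection only at scheduled draws; unscheduled tests shrink it. For TSH the gap is smaller but extends to 56 days. The change in reported incidence cannot be fixed from the documents, and the 0.5 to 5.1 points above are illustrative only.

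A reader might infer that the trial's safety conclusion for Q4W is unsound, or that the SAP certainly lacks a correction. Neither follows. The tables are descriptive, longer abnormalities are little affected, and the Core Safety SAP has not been seen. This is a point to consider for interpretation and does not affect any formal test.

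**What to change.** If the Core Safety SAP already handles unequal testing frequency, cite that rule in SAP 7.6.11. If not:

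- Keep the full worst-grade table.
- Add a supplementary worst-grade table for hematology, chemistry and liver tests with one spacing rule in both arms. Start from the Cycle 1 pre-dose sample, which is baseline and is not counted. Then keep the first available sample, scheduled or dose-delay re-evaluation, taken at least 26 days (28 minus the 2-day visit window) after the last kept sample. Choose by date, never by value. Add Follow-Up Visit 1 and 2 samples in both arms, within the SAP 6.1.2 window.
- Do not select Arm 1 samples by odd cycle number.
- Report tests per subject by arm for every panel, including TSH.
- State as limitations that the supplementary table does not cover TSH, that time since last dose still differs (about 14 v 28 days), and that additional standard-of-care tests may not be in the database.

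The cost is SAP wording and one set of tables from data already collected. About half of Arm 1's scheduled samples go unused in the supplementary table, so it can only sit beside the full one. An Arm 2 draw taken slightly early is skipped, and the next comes about four weeks later, so a small gap can remain. Showing the number of kept samples by arm would make that visible. No visit, test or clinical rule changes.
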